3.1.4.3 Logistic Model Used for Efficacy Analysis with Binary Variables

Treatment comparisons of categorical efficacy variables will be assessed using a logistic regression analysis with treatment in the model. The proportions and 95% CI (Clopper-Pearson (exact) method) will be reported. For each treatment comparison, an estimate of the odds ratio, corresponding Wald 95% CI, and p-value will be presented.

3.1.4.4 Mixed-effects Model of Repeated Measures (MMRM) Used for Efficacy Analysis with Continuous Variables

Treatment comparisons of continuous efficacy variables will be assessed using MMRM analysis at all visits including unscheduled visits prior to or at Week 52.

When the MMRM model is used the model includes treatment, visit and treatment*visit interaction as fixed effects, and subject as random effect. For other efficacy variables, the model includes treatment, week, and baseline values as fixed effects, and subject as random effect. For the CRISS Score if the data is not normally distributed then the rank-transformed values will be used instead. The covariance structure to model the within-patient errors will be unstructured. If the unstructured covariance matrix results in a lack of convergence, the heterogeneous Toeplitz covariance structure, followed by the heterogeneous autoregressive covariance structure, followed by compound symmetry will be used. The Newton-Raphson with ridging optimization technique will be used to aid with convergence. The Kenward-Roger method will be used to estimate the denominator degrees of freedom. Type III tests for the LSM will be used for the statistical comparison; the 95% CI will also be reported. Below is the SAS code for the MMRM analysis.

```
Proc mixed DATA=XX;
Class USUBJID TRT AVISITN;
Model AVAL = TRT AVISITN TRT*AVISITN/ ddfm=KENWARDROGER;
```

```
Repeated AVISITN/Subject=USUBJID type=UN;
lsmeans TRT*AVISITN/diff=control cl alpha=0.05;
Run;
```

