3.8 Definition of Efficacy Endpoints

3.8.1 Primary Efficacy Endpoint: CRISS

The primary efficacy endpoint is Combined Response Index in Diffuse Cutaneous Systemic Sclerosis (CRISS).

CRISS is a 2-step process for use in a clinical trial.

Step 1: patients who develop new onset of renal crisis, new onset or worsening of lung fibrosis, new onset of pulmonary arterial hypertension, new onset of left ventricular failure during the trial are considered as not improved and assigned a probability of improving equal to 0.0.

Step 2: For the remaining patients, step 2 involves computing the predicted probability of

improving for each individual, using the equation shown below.

$$\frac{\exp\left[-5.54 - 0.81 * \Delta_{MRSS} + 0.21 * \Delta_{FVC\%} - 0.40 * \Delta_{Pt-glob} - 0.44 * \Delta_{MD-glob} - 3.41 * \Delta_{HAQ-DI}\right]}{1 + \exp\left[-5.54 - 0.81 * \Delta_{MRSS} + 0.21 * \Delta_{FVC\%} - 0.40 * \Delta_{Pt-glob} - 0.44 * \Delta_{MD-glob} - 3.41 * \Delta_{HAQ-DI}\right]}$$

where Δ_{MRSS} indicates the change in mRSS from baseline to follow up, $\Delta_{FVC\%}$ denotes the change in FVC% predicted from baseline to follow up, $\Delta_{Pt-glob}$ indicates the change in patient global assessment, $\Delta_{MD-glob}$ denotes the change in physician global assessment, and Δ_{HAQ-DI} is the change in HAQ-DI. All changes are absolute change (Time₂-Time_{baseline}).

As patient global assessment and physician global assessment are based on a VAS of 0 (Extremely Poor)-100 (Excellent) in CRF. When calculating the CRISS score, these 2 scores should be divided by 10 firstly to make it in a 0-10 scale. If any of the component scores are missing, CRISS score will be calculated based on the imputed component score using LOCF method.

The outcome is a continuous variable between 0.0 and 1.0 (0-100%). A higher score indicates greater probability of improvement. A CRISS score ≥ 20% is considered as the minimal detectable difference and will be described as CRISS20 in the SAP. A CRISS score >= 60% is considered as the minimally important difference and will be described as CRISS60 in the SAP. This will be the primary variable for efficacy.

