Analyses of the primary efficacy endpoints will be conducted using the mITT population. The number and percentage of patients achieving CRISS60 response will be summarized by treatment group. Treatment comparisons between each belumosudil dose regimen and placebo in the proportion of patients achieving an CRISS60 response will be analyzed using a logistic regression analysis with treatment in the model.

The continuous CRISS score will be summarized as a continuous endpoint at all post baseline scheduled assessment visits. The continuous CRISS score will be analyzed using the MMRM model, and a t-test comparison. If the data is not normally distributed then the Wilcoxon-Mann-Whitney model will be used instead of a t-test. Missing data will be imputed using the Linearization method The linearization method will take the average of the last observation and the next non missing observation. If there is no next non missing observation in the current treatment group then just the last observation will be used.

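### No planned CRISS analysis adjusts for any baseline value, although baseline mRSS is collected on everyone: precision may be lost, and chance imbalance stays uncorrected

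*SAP*

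**What the plan says.** SAP 3.8.1 makes CRISS the primary endpoint. After defining CRISS20 and then CRISS60 it adds "This will be the primary variable for efficacy", which read literally points to CRISS60. The proportion reaching CRISS60 "will be analyzed using a logistic regression analysis with treatment in the model"; no other term is listed. For the score itself, "The continuous CRISS score will be analyzed using the MMRM model, and a t-test comparison", with Wilcoxon-Mann-Whitney replacing the t-test if the data are not normal.

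SAP 3.1.4.4 describes the MMRM in two consecutive sentences. The first is "When the MMRM model is used the model includes treatment, visit and treatment*visit interaction as fixed effects, and subject as random effect". The second is "For other efficacy variables, the model includes treatment, week, and baseline values as fixed effects, and subject as random effect". The first does not name the endpoint it governs; the contrast with other variables implies CRISS. The only code printed for the MMRM is "Model AVAL = TRT AVISITN TRT*AVISITN/ ddfm=KENWARDROGER", which has no baseline term.

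SAP 3.1.4.5 adds an ANCOVA with treatment and baseline for continuous efficacy variables. The secondary-endpoint sections call on it for mRSS, FVC and the global assessments, but 3.8.1 does not call on it for CRISS. Protocol 9.8.4 lists only treatment and week as fixed effects.

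Protocol 5.2.1 and Appendix A (footnote d) schedule mRSS on Day 1 for all subjects. It is also measured at screening, because Protocol 3.4 restricts entry to mRSS 15 to 35. Protocol 4.3 and 5.2 describe 1:1:1 randomisation and mention no stratification factor.

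**The concern.** The secondary continuous endpoints are adjusted for baseline and the primary one is not, with no reason given. Two things are at stake.

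- **Precision.** If baseline mRSS predicts CRISS, an unadjusted comparison of 20 with 20 gives wider intervals than the same data could support. Protocol 9.7.1 says the trial's main purpose is to guide later studies, so the estimate and its interval are its product.
- **Chance imbalance.** With small arms and no stated stratification, the arms can differ in baseline mRSS by luck. If no covariate is named beforehand, any adjustment made after seeing such a gap is post hoc.

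Separately, the text and code of SAP 3.1.4.4 disagree. A programmer who follows the printed model would drop baseline from the MMRM for every endpoint, including those where the text requires it.

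**Working it through.** **Figures in the plan.** Neither document states an efficacy power, a CRISS standard deviation or a target precision. The only probabilities attached to 20 per group concern adverse events, and they reproduce: 1 − 0.86^20 = 95.1% (stated as above 90%) and 1 − 0.90^20 = 87.8% (stated as above 80%). They do not bear on this point.

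**Does CRISS have a usable baseline of its own?** In the SAP 3.8.1 equation with every change set to zero, CRISS = exp(−5.54) / (1 + exp(−5.54)) = 0.0039 for every subject. A constant cannot act as a covariate. So even if the second sentence of 3.1.4.4 or the ANCOVA of 3.1.4.5 were meant to cover CRISS, its baseline term would do nothing. Only the baseline of a component can help.

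**Gain for the continuous score.** Inputs: N = 60, three arms of 20, two-sided 0.05 (SAP 3.1.3 and 3.1.4.4). Assumptions: the correlation ρ of baseline mRSS with Week 24 CRISS, and an effect of 0.8 SD for the power column. The calculation treats Week 24 as a single-visit comparison with one covariate, which approximates the MMRM.

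Variance ratio, adjusted to unadjusted = (1 − ρ²) × (1 + 1/(60 − 3 − 2)) = (1 − ρ²) × 1.018. The second factor is the cost of estimating one covariate.

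| ρ (assumed) | Variance ratio | CI width ratio | Power at 0.8 SD |
|---|---|---|---|
| unadjusted | 1 | 1 | 70.1% |
| 0 | 1.018 | 1.009 | 69.3% |
| 0.2 | 0.977 | 0.989 | 71.0% |
| 0.3 | 0.927 | 0.963 | 73.3% |
| 0.4 | 0.855 | 0.925 | 76.7% |

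Break-even in the three-arm model is where (1 − ρ²) × 56/55 = 1, so ρ = √(1/56) = 0.13. With two arms only it is √(1/37) = 0.16.

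**What correlation is plausible?** An illustrative simulation used the SAP's CRISS equation. It assumed baseline mRSS uniform on 15 to 35, mean mRSS change −3 or −6 with residual SD 5 or 7, 0 to 0.45 units more improvement per unit of baseline mRSS, and the other component changes unrelated to baseline mRSS. The correlation with CRISS came out between 0 and 0.40, which is the range tabulated. It depends wholly on the assumed slope.

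**Chance imbalance.** If baseline mRSS is uniform on 15 to 35 (assumed), its SD is 20/√12 = 5.8. The SE of a 20 v 20 difference in means is 5.8 × √(2/20) = 1.8 units. A gap above 2 units then arises in about 27% of randomisations for any one comparison.

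**CRISS60.** The 1 − ρ² factor belongs to linear models and does not carry over to logistic regression. Simulated at 20 v 20 with assumed response rates of 35% and 70%, about 3,000 runs per row:

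| Log-odds slope per SD of baseline (assumed) | Mean SE, unadjusted → adjusted | Power, unadjusted → adjusted |
|---|---|---|
| 0 | 0.71 → 0.74 | 57.5% → 58.9% |
| 0.3 | 0.71 → 0.75 | 58.3% → 60.8% |
| 0.6 | 0.71 → 0.80 | 57.3% → 62.1% |
| 1.0 | 0.71 → 0.90 | 56.2% → 65.6% |

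The SE of the log odds ratio widens in every row, because the adjusted odds ratio is conditional on baseline. Power rises modestly. The small rise at slope 0, where there is nothing to gain, shows that not all of it is real.

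**The case against.** The trial is exploratory, its sample size is not driven by a hypothesis test, and randomisation keeps the unadjusted comparison valid. No stated figure becomes wrong. The other endpoints are adjusted for their own baselines and CRISS has none, so leaving it unadjusted is not plainly inconsistent; choosing mRSS over FVC, HAQ-DI or the global assessments is a judgement. All of this stands, and it limits the weight of the point. It does not remove the point: intervals and p-values will be reported, and naming one covariate in advance is cheap.

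A reader might infer more than the documents support:

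- **That precision is certainly given away.** The correlation is not in either document, and below about 0.13 to 0.16 adjustment costs a little.
- **That mRSS is the strongest component because its coefficient is 0.81 per unit.** The HAQ-DI coefficient is 3.41. Ranking the components needs the SDs of their changes, which are not given.
- **That entry at 15 to 35 caps the score through a floor effect.** With the other components unchanged, CRISS reaches 60% after a fall of (5.54 + 0.405)/0.81 = 7.3 units, and a fall of 15 gives 0.999. Even the lowest-entry subject has room. The same 7.3 units are 49% of a score of 15 and 21% of a score of 35, so dependence on baseline is plausible, but it is not shown.
- **That a baseline-by-visit term costs one degree of freedom.** Appendix A schedules CRISS at seven on-treatment visits (Weeks 8, 16, 24, 28, 36, 44 and 52). That means seven slopes, beside an unstructured covariance with 7 × 8/2 = 28 parameters.

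**Conclusion.** The point holds in a limited form. Every planned CRISS analysis omits baseline, a covariate is available for every subject, and the SAP's general baseline term cannot do the job for CRISS. For the continuous score the consequence ranges from a variance increase of about 2% if baseline mRSS is unrelated to CRISS to a reduction of about 14% at an assumed correlation of 0.4. The benefit is therefore small to moderate, and it rests on a correlation that the documents do not supply. Pre-specified adjustment for chance imbalance in baseline mRSS is a further reason to act. For CRISS60 the documents and calculations support at most a small power gain with a conditional odds ratio, not better precision. The mismatch between the MMRM text and its code needs no assumption and should be corrected in any case.

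**What to change.** 1. In SAP 3.8.1 and 3.1.4.4, pre-specify baseline mRSS as a single continuous covariate in the MMRM for the continuous CRISS score. If CRISS is rank-transformed, rank the covariate too. A baseline-by-visit term is not required.
2. Keep the t-test or Wilcoxon test as unadjusted sensitivity analyses.
3. State which of the two MMRM sentences in 3.1.4.4 applies to CRISS.
4. Add `BASE` to the printed MMRM code for the other endpoints, so that it matches the text.
5. If a baseline-adjusted logistic model for CRISS60 is added, describe it as a possible small power gain with a conditional odds ratio, or report a standardised risk difference. Do not describe it as a precision gain.

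The cost is SAP wording and one coefficient in the CRISS model. No new data are needed, since eligibility already requires an mRSS for every subject. The downside is about 1.8% more variance, or intervals about 0.9% wider, if baseline mRSS turns out to be unrelated to CRISS. The change should be fixed before results by arm are seen.

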3.8.2 Secondary Efficacy Endpoints

3.8.2.1 mRSS

The mRSS is a measure of skin thickness rated with scores ranging from zero (0; normal) to three (3; severe skin thickening) across 17 different sites. The total score is the sum of the individual skin scores in the 17 body areas (e.g., face, hands, fingers; proximal area of the arms, distal area of the arms, thorax, abdomen; proximal area of the legs, and distal area of the legs, feet), giving a range of 0-51 units. A negative change from baseline demonstrates improvement.

MRSS total score, change from baseline, percent improvement will be summarized as a continuous endpoint at all scheduled assessment visits.

The change from baseline and percent improvement in mRSS total score will be analyzed using the MMRM model. In addition, the change from baseline and percent improvement in mRSS total score will be analyzed using the ANCOVA model. Missing data will not be imputed.

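### SAP 3.1.4.4 lists two sets of MMRM fixed effects without saying which applies to mRSS, FVC%, the two global assessments and SHAQ-DI, and neither gives a baseline-adjusted Week 24 contrast

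*SAP*

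**What the plan says.** SAP 2.1.2 sets the secondary comparison for mRSS, FVC, the physician and patient globals and SHAQ-DI as belumosudil against placebo at Week 24.

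SAP 3.1.4.4 gives two lists of fixed effects in consecutive sentences.

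- List A: "When the MMRM model is used the model includes treatment, visit and treatment*visit interaction as fixed effects, and subject as random effect". There is no baseline term.
- List B: "For other efficacy variables, the model includes treatment, week, and baseline values as fixed effects, and subject as random effect". There is no treatment-by-visit term.

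The only MMRM code follows list A. Its model line is "Model AVAL = TRT AVISITN TRT*AVISITN/ ddfm=KENWARDROGER" and its contrast line is "lsmeans TRT*AVISITN/diff=control cl alpha=0.05". On the data used, the section says that comparisons "will be assessed using MMRM analysis at all visits including unscheduled visits prior to or at Week 52".

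SAP 3.8.2.1 to 3.8.2.5 do not restate the fixed effects. For mRSS: "The change from baseline and percent improvement in mRSS total score will be analyzed using the MMRM model". FVC%, the two globals and SHAQ-DI have parallel sentences. SAP 3.8.1 refers to the model for CRISS in the same way: "The continuous CRISS score will be analyzed using the MMRM model, and a t-test comparison".

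SAP 3.1.4.5 adds an ANCOVA with treatment and baseline. It names no visit. Missing values of the five secondary endpoints are not imputed. In the SHAQ-DI section, the ANCOVA sentence names the patient global score instead.

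**The concern.** Two programmers could each follow SAP 3.1.4.4 faithfully and report different estimates. The wording of 3.8.2 points to list A. But the five endpoints are also efficacy variables other than CRISS, which points to list B. A split between CRISS and the rest would make sense, because CRISS is built from changes ("All changes are absolute change") and has no baseline value of its own, but the SAP does not say that this is meant. Protocol 9.8.4 does not settle it, since it gives a third form with treatment and week only.

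Each list lacks one term needed for the stated objective. List A forgoes the precision available from baseline, with only 20 subjects per arm. List B imposes one treatment difference on all visits, so it does not estimate a Week 24 effect. The printed least-squares-means line also requests `TRT*AVISITN`, an effect that list B does not contain. What is at stake is the size and precision of estimates that, by Protocol 9.7.1, are meant to guide follow-up studies.

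**Working it through.** The plan gives no effect size, covariance or dropout figure for these endpoints, so there is no stated figure to reproduce. The inputs from the documents are 3 arms of 20 (SAP 3.1.3) and efficacy visits at Weeks 8, 16 and 24 up to the target visit (Protocol Appendix A). Correlations, effect profiles and missingness below are assumptions.

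**List A: precision lost by omitting baseline.** Let r be the correlation between baseline and change. With complete data, the variance ratio (adjusted to unadjusted) is (1 − r²)(1 + 1/55), where 55 = 60 − 3 − 2. The CI width ratio is its square root.

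| r | Variance ratio | CI width ratio |
|---|---|---|
| 0.3 | 0.927 | 0.963 |
| 0.4 | 0.855 | 0.925 |
| 0.5 | 0.764 | 0.874 |

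Adding baseline would therefore narrow the 95% CI by about 4% to 13%. A simulation of 20,000 trials gave the same width ratios. Under randomization, the expected value of the list A contrast is the Week 24 effect.

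**List B: what the single treatment effect estimates.** Let V be the covariance of the three visits given baseline and d the treatment differences by visit. The additive model estimates w′d, with w = V⁻¹1 / (1′V⁻¹1).

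- Compound symmetry gives weights of 1/3 each, whatever the correlation.
- AR(1) with correlation ρ per 8 weeks gives w proportional to (1 − ρ + ρ², (1 − ρ)², 1 − ρ). For ρ = 0.7 this is (0.79, 0.09, 0.30)/1.18 = (0.669, 0.076, 0.254).

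With d expressed as a share of the Week 24 effect, a linear build is (1/3, 2/3, 1) and an early plateau is (0.60, 0.85, 1.00). For ρ = 0.7 and a linear build, the estimate is 0.669/3 + 0.076 × 2/3 + 0.254 = 0.53.

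| Covariance | Linear build | Early plateau | Constant |
|---|---|---|---|
| Compound symmetry | 0.67 | 0.82 | 1.00 |
| AR(1) 0.5 | 0.61 | 0.78 | 1.00 |
| AR(1) 0.7 | 0.53 | 0.72 | 1.00 |
| AR(1) 0.9 | 0.40 | 0.64 | 1.00 |

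The last AR(1) row is an edge case. With ρ = 0.9 and no visit-level noise, 0.91/1.02 = 89% of the weight falls on Week 8. If 10% / 20% / 30% of the variance is visit-specific noise, the linear-build share rises to 0.52 / 0.58 / 0.61.

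**ANCOVA at Week 24 against an MMRM with baseline and treatment-by-visit.** With complete data, the ANCOVA recovers the baseline gain in full. Suppose a fraction p lacks Week 24 at random after Week 16. Let R² be the share of Week 24 variance, given baseline, that Weeks 8 and 16 explain. The CI width ratio is √{[1/(1 − p)] / [(1 − R²)/(1 − p) + R²]}.

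- Compound symmetry 0.5: the conditional correlation is 0.25/0.75 = 1/3, so R² = 2(1/9)/(4/3) = 0.167. The ratios are 1.008 / 1.017 / 1.026 for p = 0.1 / 0.2 / 0.3.
- AR(1) 0.7: R² = 1 − 0.51/0.882 = 0.422. The ratios are 1.022 / 1.045 / 1.070.

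The ANCOVA interval is thus about 1% to 7% wider than that of the full MMRM.

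**The case against.** The strongest reply is that the analysis set as a whole already contains a baseline-adjusted comparison. SAP 3.1.4.5 specifies an ANCOVA for continuous efficacy variables, and 3.8.2.1 to 3.8.2.4 assign it to mRSS, FVC% and both globals. SHAQ-DI falls under the general sentence in 3.1.4.5, and the wrong endpoint name in its own section looks like a copying slip. The objective and the first analysis period both point to Week 24. Most of this stands. A reader might infer that the plan yields no baseline-adjusted Week 24 estimate at all, and the documents do not support that. The gap is in the MMRM, and the ANCOVA still needs its visit stated.

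A second reply is that list A has the better textual claim, because it is the coded version and 3.8.2 uses the same name for the model. On that reading the only loss is precision. This is fair, but the wording of list B keeps the other reading open. If list A is in fact meant for CRISS alone, all five secondary endpoints receive the model that has no Week 24 contrast.

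A reader might also infer from the reference to all visits up to Week 52 that the placebo comparison would pool visits after placebo subjects switch to belumosudil. SAP 2.4 limits the placebo label to the first 28 weeks and gives switched subjects their own labels, and SAP 3.1.1 splits the analysis into periods, one of them Weeks 0 to 24. Both point away from pooling. Its effect would also depend on how fast placebo subjects catch up, which the documents do not say, so no figure is given for it here.

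Finally, the study is exploratory and no formal test depends on these endpoints. That limits the weight of the point but does not remove it, since the estimates themselves are the product.

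**Conclusion.** The inconsistency is real: no MMRM in the SAP, as written, contains both a baseline term and a treatment-by-visit term. If list A applies, the Week 24 estimate is unbiased and its 95% CI could be about 4% to 13% narrower. If list B applies, the estimate equals the Week 24 effect only when the difference is constant over visits. It is about 0.53 to 0.67 of that effect for a linear build under compound symmetry or AR(1) up to 0.7, and 0.64 to 0.82 for an early plateau. The value of 0.40 should not be read as typical, because it needs AR(1) 0.9 with no visit-level noise. All these sizes rest on assumed correlations and effect profiles.

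An ANCOVA run at Week 24 largely fills the gap, at the cost of an interval about 1% to 7% wider when 10% to 30% are missing at random. The effect on conclusions is therefore modest. The point lies between minor and should-fix, and the text is worth correcting because the correction costs little.

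**What to change.** - For mRSS, FVC%, both globals and SHAQ-DI, specify one MMRM with treatment, visit, treatment-by-visit and baseline (baseline-by-visit optional), and add `BASE` to the code.
- State that the version without baseline applies to CRISS only.
- Use scheduled double-blind visits for the between-arm comparison.
- Obtain each dose-versus-placebo difference at Week 24 with a contrast that fixes both the placebo arm and the Week 24 visit. Naming placebo alone in `diff=control` is not enough, because the control for `TRT*AVISITN` is a single treatment-by-visit cell.
- State that the ANCOVA is run at Week 24, and correct the endpoint named in the SHAQ-DI ANCOVA sentence.

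The cost is SAP wording, a few lines of code and a few degrees of freedom. Baseline is already collected, so no new data are needed.

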2 STUDY SUMMARY

2.1 Study Objectives

2.1.1 Primary objective

 To evaluate the efficacy of belumosudil compared to placebo for the Combined Response Index in diffuse cutaneous Systemic Sclerosis (CRISS) at Week 24 in modified Intent-to-Treatment (mITT) population.

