2.4 Treatment Descriptions

The treatment groups will be described below and used for different analysis.

KQD: KD025 200mg QD for the first 28 weeks

KBID: KD025 200mg BID for the first 28 weeks

PBO: Placebo for the first 28 weeks

KQD/KQD: KD025 200mg QD for the first 28 weeks and KD025 200mg QD from week 28 to 52.

KBID/KBID: KD025 200mg BID for the first 28 weeks and KD025 200mg BID from week 28 to 52.

K: KD025 200mg for the first 28 weeks

PBO/KQD: Placebo for the first 28 weeks and KD025 200mg QD from week 28 to 52.

PBO/KBID: Placebo for the first 28 weeks and KD025 200mg BID from week 28 to 52.

KQD_C: KD025 200mg QD for the first 28 weeks combined with subjects that switched from placebo to KD025 200mg QD from week 28 to 52.

KBID_C: KD025 200mg BID for the first 28 weeks combined with subjects that switched from placebo to KD025 200mg BID from week 28 to 52.

K_C: KD025 200mg for the first 28 weeks combined with subjects that switched from placebo to KD025 200mg from week 28 to 52.

All KD025 200mg QD: KD025 200mg QD for the first 52 weeks combined with subjects that switched from placebo to KD025 200mg QD from week 28 to 52.

All KD025 200mg BID: KD025 200mg BID for the first 52 weeks combined with subjects that switched from placebo to KD025 200mg BID from week 28 to 52.

All KD025: KD025 200mg for the first 52 weeks combined with subjects that switched from placebo to KD025 200mg from week 28 to 52.

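### The MMRM code compares every treatment-by-visit mean with one fixed cell, so it does not print the belumosudil-placebo contrasts at Week 24

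*SAP*

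**What the plan says.** The primary objective in SAP 2.1.1 is "To evaluate the efficacy of belumosudil compared to placebo for the Combined Response Index in diffuse cutaneous Systemic Sclerosis (CRISS) at Week 24". For the continuous score, SAP 3.8.1 states: "The continuous CRISS score will be analyzed using the MMRM model, and a t-test comparison", with a Wilcoxon-Mann-Whitney test replacing the t-test if the data are not normal. SAP 3.8.2.1 to 3.8.2.5 apply the MMRM to mRSS, FVC%, both global assessments and SHAQ-DI.

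SAP 3.1.4.4 describes the intended use: "Treatment comparisons of continuous efficacy variables will be assessed using MMRM analysis at all visits including unscheduled visits prior to or at Week 52". It then gives the code. The class line is "Class USUBJID TRT AVISITN", the model line is "Model AVAL = TRT AVISITN TRT*AVISITN/ ddfm=KENWARDROGER", and the contrast line is "lsmeans TRT*AVISITN/diff=control cl alpha=0.05". The code sets no reference level or sort option, and it has no ESTIMATE, LSMESTIMATE or SLICE statement.

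SAP 2.4 gives descriptive treatment labels, for example "PBO: Placebo for the first 28 weeks", but no numeric codes or order. No other part of the SAP names a control cell or restricts differences to the same visit.

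**The concern.** The `diff=control` option compares each level of the stated effect with one control level of that same effect. Here the effect is the treatment-by-visit interaction, so the control is one arm at one visit, not the placebo arm visit by visit. A single fixed cell can be the same-visit comparator at one visit at most, whereas the text promises treatment comparisons at every visit.

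Two things are at stake. The MMRM inference for each dose against placebo at Week 24 would be missing from the output. The rows that look most like it, such as a belumosudil arm at Week 24 minus placebo at Week 8, would combine any treatment effect with change over time. The Type III tests mentioned in the text do not fill the gap: in this model they are joint tests of treatment, visit and interaction, not a Week 24 dose-placebo difference.

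**Working it through.** The plan states no figure to reproduce here. The check is to list which contrasts the line generates.

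**Inputs**
- Arms: KQD, KBID and PBO (SAP 2.4).
- Post-baseline efficacy visits: Weeks 8, 16, 24, 28, 36, 44 and 52 (Protocol Appendix A, schedule and footnote d).
- Visit sets: to Week 24, to Week 28 and to Week 52, matching the three analysis periods in SAP 3.1.1.
- Software rule: with no level named, `diff=control` takes the first level of the effect. This is an assumption about standard PROC MIXED behaviour; SAS was not run.

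**Counting.** With 3 arms and V visits there are 3V cells. One is the control, so 3V − 1 differences are printed. Of these, 2 are at the control cell's visit, V − 1 are in the control cell's arm at another visit, and 2(V − 1) differ in both arm and visit.

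| Visits | Cells | Printed | Same visit | Same arm, other visit | Arm and visit both differ | Dose v placebo at Week 24 |
|---|---|---|---|---|---|---|
| 8, 16, 24 | 9 | 8 | 2 | 2 | 4 | 0 |
| 8 to 28 | 12 | 11 | 2 | 3 | 6 | 0 |
| 8 to 52 | 21 | 20 | 2 | 6 | 12 | 0 |

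So all but two rows compare different visits: 6 of 8, 9 of 11 and 18 of 20.

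**Does the coding matter?** Three treatment orders were tried with each visit set.
- KBID, KQD, PBO (alphabetical): the control is KBID at Week 8. The only same-visit row involving placebo is PBO minus KBID at Week 8.
- KQD, KBID, PBO: the control is KQD at Week 8. The only such row is PBO minus KQD at Week 8.
- PBO first: the control is PBO at Week 8. Both same-visit rows are dose minus placebo, at Week 8.

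In all nine combinations, no row is a dose against placebo at Week 24. If baseline records are kept, the control moves to baseline. If visits sort as text rather than as numbers, Week 16 comes first. Neither gives Week 24.

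**Illustration of a mixed row** (assumed values, not from the documents). Suppose there is no treatment effect, all arms shift by a common 2 units from Week 8 to Week 24, there are 20 per arm, and the SD is the same at both visits. The row for a dose at Week 24 minus placebo at Week 8 then has expected size 2, while the true Week 24 contrast is 0. The two cells come from different arms, so SE = SD × √(2/20). By the normal approximation, the chance of two-sided p < 0.05 is about 1 − Φ(1.96 − 2/SE):
- SD 4: SE 1.265, 1 − Φ(0.379) ≈ 35%
- SD 6: SE 1.897, 1 − Φ(0.906) ≈ 18%
- SD 8: SE 2.530, 1 − Φ(1.169) ≈ 12%

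The nominal rate is 5%.

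**The case against.** The strongest reply is that this is template code. It uses placeholder names and omits the baseline term that the text of 3.1.4.4 requires for endpoints other than CRISS. The intent to compare treatments by visit is clear from the prose, and a programmer would soon see that the output lacks same-visit rows after the control visit. The study is also exploratory, its sample size is not based on hypothesis testing (SAP 3.1.3), and no stated decision rule depends on an MMRM p-value. All of this stands, and it limits the weight of the point. It does not remove it: the SAP presents these lines as the code for the MMRM analysis and corrects them nowhere.

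Two stronger readings are tempting, and the documents do not support them.

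A reader might infer that the belumosudil-placebo comparison on the primary endpoint is lost. It is not. SAP 3.8.1 also specifies a logistic regression of CRISS60 for each dose against placebo, and a t-test or Wilcoxon comparison of the continuous score. Neither uses this line. The ANCOVA code in 3.1.4.5 requests pairwise treatment differences and is sound in this respect. It is named for mRSS, FVC% and both global assessments. It is not named for CRISS in 3.8.1, and the ANCOVA sentence in the SHAQ-DI section refers to the patient global assessment.

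A reader might also infer that an active arm will serve as control. That follows only if the labels sort alphabetically or a belumosudil arm is coded first. Placebo could equally be coded first, and the defect would remain.

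**Conclusion.** The point holds as a mismatch between the MMRM code and the SAP's own text and objective. Run as written, the code omits the standard error, confidence interval and p-value for both Week 24 dose-placebo contrasts, under every treatment order and visit set tried. The Week 24 point differences can still be obtained by subtracting printed least-squares means, because the fitted model is correct in this respect.

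The scope is the MMRM output for continuous CRISS (including its rank-transformed form) and for the secondary endpoints in SAP 3.8.2.1 to 3.8.2.5. The conclusion rests on the default control rule of the software and on Week 24 not being the first-sorted visit, which the visit schedule supports. The 12% to 35% range shows what misreading a mixed row could do under assumed values; it does not predict this trial's error rate. The code should be corrected before analysis, but this is not a flaw in the design or in the other primary-endpoint analyses.

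**What to change.** Replace the contrast line with same-visit contrasts of KQD minus PBO and KBID minus PBO at each double-blind efficacy visit: 2 doses × 4 visits (Weeks 8, 16, 24, 28) = 8 contrasts. There is no placebo arm after Week 28, so these comparisons end there. Either of two routes works:
- write the contrasts as LSMESTIMATE or ESTIMATE statements; or
- request all pairwise differences and keep only the same-visit dose-placebo rows, checking the sign. With these four visits that means keeping 8 of 12 × 11 / 2 = 66 differences.

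State in the SAP that the two Week 24 contrasts are the main MMRM comparisons, and give the treatment and visit codes.

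Naming placebo at Week 24 as the control cell, for example `diff=control('PBO' '24')` with the actual codes, is enough for Week 24 only. Its other rows would still compare different visits, apart from those at Week 24, and should not be reported as treatment effects.

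The cost is a few lines of code and one or two sentences of text. Data collection, sample size and the fitted model do not change.
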